8.3 Lost to Follow-up

- All reasonable efforts must be made to locate participants to determine and report their ongoing status. This includes follow-up with persons authorized by the participant.
- Lost to follow-up is defined by the inability to reach the participant after a minimum of three documented phone calls, faxes, or emails as well as lack of response by participant to one registered mail letter. All attempts should be documented in the participant's medical records.
- If it is determined that the participant has died, the site will use permissible local methods to obtain date and cause of death.
- If investigator's use of third-party representative to assist in the follow-up portion of the study has been included in the participant's informed consent, then the investigator may use a Sponsor retained third-party representative to assist site staff with obtaining participant's contact information or other public vital status data necessary to complete the follow-up portion of the study. The site staff and representative will consult publicly available sources, such as public health registries and databases, in order to obtain updated contact information.
- If after all attempts, the participant remains lost to follow-up, then the last known alive date as determined by the investigator should be reported and documented in the participant's medical records.

9 STUDY ASSESSMENTS AND PROCEDURES

Study procedures and timing are summarized in the Schedule of Activities ([Section 2](#)). Protocol waivers or exemptions are not allowed. Adherence to the study design requirements, including those specified in the Schedule of Activities ([Section 2](#)), is essential and required for study conduct.

All screening evaluations must be completed and reviewed to confirm that potential participants meet all eligibility criteria before randomization. The investigator will maintain screening log to record details of all participants screened and to confirm eligibility or record reasons for screening failure, as applicable.

Procedures conducted as part of the participant's routine clinical management (eg, blood count) and obtained before signing of informed consent may be utilized for screening or baseline purposes

provided the procedure meets the protocol-defined criteria and has been performed within the timeframe defined in the Schedule of Activities ([Section 2](#)).

All immediate safety concerns must be discussed with the Sponsor immediately upon occurrence or awareness to determine if the participant should continue or discontinue treatment.

Additional measures, including non-study required laboratory tests, should be performed as clinically indicated or to comply with local regulations. Laboratory toxicities (eg, suspected drug induced liver enzyme evaluations) will be monitored during the follow-up phase via on-site/local labs until all study drug-related toxicities resolve, return to baseline, or are deemed irreversible.

If a participant shows pulmonary-related signs (hypoxia, fever) or symptoms (eg, dyspnea, cough, and fever) consistent with possible pulmonary AEs, the participant should be immediately evaluated to rule out pulmonary toxicity, according to the suspected pulmonary toxicity management algorithm in the BMS-936558 (nivolumab) Investigator's Brochure.

Some of the assessments referred to in this section may not be captured as data in the eCRF. They are intended to be used as safety monitoring by the treating physician. Additional testing or assessments may be performed as clinically necessary or where required by institutional or local regulations.

9.1 Efficacy Assessments

Per Protocol Amendment 04, tumor assessments will be determined by investigator.

9.1.1 Definition of Events in EFS

EFS is defined as the time from randomization to any of the following events: progression of disease that precludes surgery, local or distant recurrence, or death due to any cause. Details on EFS events are provided below:

- Worsening of disease that precludes surgery (as determined by Investigator or [Section 9.1.1.2](#))
- If surgery is possible, but not performed for other reasons (eg, participant refuses, AEs), and there has been RECIST v1.1 assessed progression in the neoadjuvant period, then it will be considered an EFS event (see [Section 9.1.2.2](#)).
- If surgery is possible but not performed for other reasons (participant refuses or worsening of medical condition), then the participant may continue on study treatment and will be considered to have an EFS event if and when:
 - There is RECIST v1.1 defined progression
 - If there is carcinoma in situ (CIS), high grade Ta, T1, or \geq T2 disease at any time after neoadjuvant therapy is completed observed on cystoscopy and confirmed by pathologic review after TURBT and/or bladder biopsy (see schedule of cystoscopy in [Section 2](#))
- If surgery is attempted but gross resection is abandoned, due to unresectable tumor or worsening of disease, then that will be considered an EFS event.
- If RC is completed with no or only microscopic residual disease (positive margins, not visible on imaging), then the participant will continue on study and will be considered to have an EFS event if and when radiographically (or by biopsy) visible recurrence occurs.

- If surgery is completed with unequivocal gross residual disease (visible on imaging or by biopsy), it will be considered as an EFS event. Equivocal residual disease should be confirmed by biopsy or confirmed by further progression (RECIST v1.1) at following scan (see [Appendix 10](#)).
- Local or distant recurrence or new upper tract tumor confirmed by imaging or biopsy
- Death due to any cause

9.1.1.1 Definition of Disease Recurrence

Bladder cancer recurrence will be defined as any unequivocal evidence of new bladder cancer lesions that are detected after RC. Biopsy should be employed where required to prove recurrence. In cases where recurrence is equivocal and biopsy cannot be performed or were not diagnostic, the participant may continue treatment and imaging of suspect lesions should be repeated in 4-8 weeks ([Section 9.1.2.3](#)).

The first post-surgery assessment will occur within 60 to 90 days after RC and prior to beginning post-surgery IO therapy for Arms A and B. Participants who have new LNs defined as short axis ≥ 10 mm with growth of ≥ 5 mm (eg, 9 mm LN grows to 14 mm) or have findings of other new, unequivocal non-nodal lesions will be considered as having recurrence. Confirmation of recurrence must be attempted as described in [Section 9.1.2.2](#).

Tumor may recur in the following sites:

- Local, urothelial tract: Any new UC in ureter or renal pelvis, including lesions thought to be a second UC primary, will be considered recurrences, as well as new CIS, Ta high grade, T1 or muscle invasive lesion in participants who do not undergo RC.
- Local, non-urothelial tract: Any new UC in pelvic soft tissue or involving pelvic nodes below the aortic bifurcation.
- Distant: Any new non-local recurrence

Unequivocal recurrence of urothelial cancer at any of these sites will be considered an EFS event requiring that study treatment be discontinued.

9.1.1.2 Definition of Disease Progression

All participants including those who did not undergo RC due to reasons other than worsening of disease precluding surgery will be followed by imaging for disease progression according to RECIST v1.1 (see [Appendix 10](#)). For participants who are undergoing surveillance cystoscopies, see [Section 9.1.1](#) above.

9.1.1.3 Definition of pCR

The pCR rate is defined as the proportion of randomized participants with absence of any cancer (T0, N0) in pathology specimens after RC, as assessed by blinded pathology review.

9.1.2 Imaging Assessment for the Study

As per Protocol Amendment 04, images will no longer be submitted to central imaging vendor.

All images will be submitted to a central imaging vendor for BICR at any time during the study. Copies of additional scans conducted at the time of UC of the bladder/MIBC diagnosis should be stored at the sites for possible future analysis, at the Sponsor's discretion. Sponsor may also request additional historical scans to clarify baseline assessment. Prior to scanning first participant, sites should be qualified and understand the image acquisition guidelines and submission process as outlined in the CA045009 Imaging Manual provided by the central imaging vendor. Screening and on study images should be acquired as outlined in Schedule of Activities ([Section 2](#)).

Tumor assessments at other time points may be performed if clinically indicated.

Tumor assessments for all participants should continue as per protocol even if dosing is delayed or discontinued. Tumor measurements should be made by the same investigator or radiologist for each assessment, whenever possible.

9.1.2.1 Methods of Measurement

Contrast-enhanced CT of the chest, abdomen, pelvis (including excretory imaging), and all other known and/or suspected sites of disease should be performed for tumor assessments. Images should be acquired with slice thickness of 5 mm or less with no intervening gap (contiguous). Every attempt should be made to image each participant using an identical acquisition protocol on the same scanner for all imaging time points. Tumor measurements should be made by the same investigator or radiologist for each assessment, whenever possible. Change in tumor measurements and tumor response to guide ongoing study treatment decisions will be assessed by the investigator using the RECIST v1.1 criteria.

If a participant has a contraindication for CT IV contrast, then a non-contrast CT of the chest and a contrast-enhanced MRI of the abdomen, pelvis, and other known/suspected sites of disease should be obtained.

If a participant has a contraindication for both MRI and CT IV contrasts, then a non-contrast CT of the chest and a non-contrast MRI of the abdomen, pelvis, and other known/suspected sites of disease should be obtained.

If a participant has a contraindication for MRI (eg, incompatible pacemaker) in addition to contraindication to CT IV contrast, then a non-contrast CT of the chest, abdomen, pelvis, and other known/suspected sites of disease is acceptable.

Use of CT component of a PET-CT scanner: Combined modality scanning such as with PET-CT is increasingly used in clinical care, and is a modality/technology that is in rapid evolution; therefore, the recommendations outlined here may change rather quickly with time. At present, low dose or attenuation correction CT portions of a combined PET-CT are of limited use in anatomically-based efficacy assessments and it is therefore suggested that they should not be substituted for dedicated diagnostic contrast enhanced CT scans for anatomically-based RECIST v1.1 measurements. However, if a site can document that the CT performed as part of a

PET-CT is of identical diagnostic quality to a diagnostic CT (with IV and oral contrast), then the CT portion of the PET-CT can be used for RECIST v1.1 measurements. Note, however, that the PET portion of the CT introduces additional data that may bias an investigator if it is not routinely or serially performed.

9.1.2.2 BICR Confirmation of Progression or Recurrence

Per Protocol Amendment 04, BICR will be discontinued and all study treatment decisions will be based on the investigator's assessment of tumor images.

See comprehensive Definition of Events in EFS ([Section 9.1.1](#)). **Not applicable per Protocol Amendment 04.** All investigator-assessed events require BICR confirmation with the exception of events from preclusion of surgery due to disease worsening or abandoned surgery do not require BICR confirmation.

Not applicable per Protocol Amendment 04. Sites should submit all scans to the central imaging vendor on a rolling basis, throughout the duration of the study. The site will inform the central imaging vendor when the investigator assessment indicates either (i) unequivocal disease progression per RECIST v1.1 criteria (for participants without RC) or (ii) unequivocal evidence of disease recurrence after RC, in order for BICR assessment of progression/recurrence to be performed. The BICR will be completed and the results provided to the site as specified in the imaging vendor documents, provided there are no pending imaging queries to the site. All details on the timelines and associated process requirements will be outlined in the Imaging Manual.

Not applicable per Protocol Amendment 04. Participants whose [progression or recurrence] is not confirmed by the BICR will be required to continue tumor assessments (if clinically feasible) according to the protocol-specified schedule ([Section 2](#)) or sooner if clinically indicated. Also, if participants discontinue treatment without radiographic [progression or recurrence], tumor assessments will continue according to the protocol-specified schedule, as noted in Schedule of Activities ([Section 2](#)) until progression has been confirmed by BICR ([Section 9.1.2.2](#)).

All study treatment decisions will be based on the investigator's assessment of tumor images and not on the BICR assessment.

9.1.2.3 Confirmation and Date of Progression or Recurrence

Per Protocol Amendment 04, BICR will be discontinued and all study treatment decisions including progression and recurrence will be based on the investigator's assessment of tumor images.

The first date when progression or recurrence was observed is taken into account regardless of the method of assessment. Therefore, recurrence will be declared for any lesion when:

- Progression or recurrence is unequivocal (eg, multiple new measurable lesions); confirmation with histology/cytology should be attempted but is not required.
- Progression or recurrence is equivocal; for example, LN only, solitary lesion, or disease in the urothelial tract, confirmation with histology/cytology should be considered if feasible. Confirmation of a defined lesion in the upper genitourinary tract may be obtained with a retrograde study and biopsy. If biopsy is not feasible, a follow-up CT or MRI scan may be used

to confirm recurrence. Follow-up (confirmatory) scan should occur 4 to 8 weeks after the initial scan. The date of the initial scan showing recurrence (or a suspect lesion, later shown to be a recurrence) will count as the date of recurrence.

- Any pathological evidence of new bladder cancer denotes recurrence.
- A suspicious urine cytology (eg, positive Urovision or similar urine assay) alone does not constitute the basis for recurrence of disease, but should prompt for further investigation, (eg, radiological confirmation). Tumor markers or auto-antibodies alone cannot be used to document recurrence. Biopsy and/or imaging is required to establish recurrence.
- If both pathology and imaging were done and recurrence or bladder cancer confirmed, the date of recurrence is the date of which ever examination came first.
- New NMIBC in participants who do not undergo RC would be progression.

[REDACTED]

[REDACTED]

[REDACTED]

[REDACTED]

[REDACTED]

[REDACTED]

[REDACTED]

[REDACTED]

[REDACTED]

[REDACTED]

9.2 Adverse Events

The definitions of an AE or SAE can be found in [Appendix 3](#).

AEs will be reported by the participant (or, when appropriate, by a caregiver, surrogate, or the participant's legally authorized representative).

The investigator and any designees are responsible for detecting, documenting, and reporting events that meet the definition of an AE or SAE and remain responsible for following up AEs that

are serious, considered related to the study treatment or the study, or that caused the participant to discontinue before completing the study.

Contacts for SAE reporting specified in [Appendix 3](#)

9.2.1 Time Period and Frequency for Collecting AE and SAE Information

Serious Adverse Drug Reactions section in the IB represent the Reference Safety Information to determine expectedness of SAEs for expedited reporting.

- The collection of non-serious AEs (with the exception of non-serious AEs related to SARS-CoV-2 infection) should begin at initiation of study treatment. All SAEs, and all AEs (SAEs and non-serious AEs) associated with confirmed or suspected SARS-CoV-2 infection must be collected from the date of the participant's written consent until 100 days following discontinuation of dosing.
- All SAEs must be collected from the time of signing the consent, including those thought to be associated with protocol-specified procedures and within 100 days of discontinuation of dosing.
- For participants randomized to treatment and never treated with study drug, SAEs should be collected for 30 days from the date of randomization. For participants in Arm C, SAEs should be collected for 100 days following RC.
- The investigator must report any SAE that occurs after these time periods and that is believed to be related to study drug or protocol-specified procedure, (eg, a follow-up skin biopsy).
- Medical occurrences that begin before the start of study treatment but after obtaining informed consent will be recorded on the appropriate section of the eCRF module.
- All SAEs will be recorded and reported to Sponsor or designee within 24 hours, as indicated in Appendix 3.
- The investigator will submit any updated SAE data to the sponsor or designee within 24 hours of updated information being available.
- CVA (any grade) is considered an AEOSI and should be assessed for seriousness using the standard seriousness definition. However, all CVAs are required to follow the timelines for SAE reporting (eg, 24 hours). CVA management guidelines, provided in [Appendix 7](#), are no longer applicable per Protocol Amendment 04.

Investigators are not obligated to actively seek AEs or SAEs in former study participants. However, if the investigator learns of any SAE, including a death, at any time after a participant has been discharged from the study, and he/she considers the event reasonably related to the study treatment or study participation, the investigator must promptly notify the sponsor.

The method of evaluating, and assessing causality of AEs and SAEs and the procedures for completing and reporting/transmitting SAE reports are provided in Appendix 3.

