Adverse Events Assessment (Including SAEs)	X	X	See Notes	SAEs to be collected after the 100-day safety visit if the SAE is deemed to be related or residual toxicities are persisting. All SAEs and non-serious AEs should be collected continuously during the treatment period and for a minimum of 100 days following discontinuation of study treatment for adjuvant therapy and 100 days following RC in participants who do not have adjuvant therapy. Participants will be followed for all SAEs, non-serious AEs of special interest (as defined in Section 9.8), and all AEs (SAEs and non-serious AEs) associated with confirmed or suspected SARS-CoV-2 infection until resolution, the condition stabilizes, the event is otherwise explained, the event is deemed irreversible, the participant is lost to follow-up (as defined in Section 8.3), or for suspected cases, until SARS-CoV-2 infection is ruled-out.
Review of Concomitant/Subsequent Medications	X	X		Record at each visit.

Table 2-4: Long-term Follow-up Assessments (Arm A and Arm B)

***Per Protocol Amendment 04, participants will discontinue from the study following one recurrence update and survival status update.**

Procedure	Follow-up Visit 1 ^{a,b}	Follow-up Visit 2 ^{a,b}	*Not applicable per Protocol Amendment 04. Survival Follow-up Every 3 Months (± 14 Days) ^{c,b}	Notes
Subsequent Anti-cancer Therapy	X	X	X	Per Protocol Amendment 04, the following will no longer be collected after 100 days of follow-up: Collect every 3 months at Survival Visits until death, lost to follow-up, withdrawal of study consent, or up to 5 years. May be performed by phone contact or office visit. Include documentation of additional subsequent cancer therapy details such as regimen, setting of the regimen, line of therapy, start date and end date of each regimen, and best response to the regimen and date of progression to subsequent anti-cancer therapies will be collected.
Laboratory Tests				
Clinical Laboratory Testing	X	Follow-up Visit 2 (if toxicities are present)		Hematology and Chemistry: See Table 9.4.7-1 .
Pregnancy Test	X	X		WOCBP only. Serum or urine pregnancy test (minimum sensitivity equivalent units 25 IU/L or equivalent units of HCG) is required.

Table 2-4: Long-term Follow-up Assessments (Arm A and Arm B)

***Per Protocol Amendment 04, participants will discontinue from the study following one recurrence update and survival status update.**

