9.2.2 Method of Detecting AEs and SAEs

Adverse events can be spontaneously reported or elicited during open-ended questioning, examination, or evaluation of a participant. Care should be taken not to introduce bias when

collecting AE and/or SAEs. Inquiry about specific AEs should be guided by clinical judgement in the context of known AEs, when appropriate for the program or protocol.

All nonserious AEs (not only those deemed to be treatment-related) should be collected continuously during the treatment period and for a minimum of 100 days following discontinuation of adjuvant therapy for Arms A and B and 100 days from RC for Arm C. For participants who do not continue adjuvant therapy in Arms A and B, AEs and/or SAEs should be collected for a period of 100 days following RC.

Every AE must be assessed by the investigator with regard to whether it is considered immune-mediated. For events which are potentially immune-mediated, additional information will be collected on the participant's case report form.

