10.2 Populations for Analyses

For purposes of main analyses, the following populations are defined:

Table 10.2-1: Analysis Populations

Population	Description
All enrolled participants	All participants who signed an informed consent form and were registered into the IRT
All randomized participants	All participants who were randomized to any treatment arm in the study
All treated participants	All randomized participants who either received at least one dose of any study medication or underwent radical cystectomy

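### Arm A/B participants who have cystectomy and no later study drug fall under conflicting AE/SAE windows, so their post-operative collection may be cut short and not match Arm C

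*Combined protocol and SAP*

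**What the plan says.** The protocol sets the safety windows in several places.

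- **Section 9.2.1, dosed participants:** all SAEs are collected from consent, "including those thought to be associated with protocol-specified procedures and within 100 days of discontinuation of dosing".
- **Section 9.2.1, randomized to treatment but undosed:** if "never treated with study drug, SAEs should be collected for 30 days from the date of randomization".
- **Section 9.2.1, Arm C:** "For participants in Arm C, SAEs should be collected for 100 days following RC". Table 2-5 uses the same end point for AEs and SAEs together.
- **Section 9.2.1, after the windows close:** "The investigator must report any SAE that occurs after these time periods and that is believed to be related to study drug or protocol-specified procedure".
- **Section 9.2.2, Arms A and B without continued adjuvant therapy:** "AEs and/or SAEs should be collected for a period of 100 days following RC".
- **Table 2-4, adverse event note:** "100 days following RC in participants who do not have adjuvant therapy".
- **Table 2-4, Survival Status row, as amended by Amendment 04:** participants leave the study once 100 days from last dose have passed. Footnote a and Section 5.1.3 also time both follow-up visits from the last dose.
- **Synopsis and Section 5.1, Amendment 04 exit rules:** the 100 days for Arm C are tied to RC. For Arms A and B no starting point is given.
- **Table 10.2-1:** the all treated population is everyone randomized who "received at least one dose of any study medication or underwent radical cystectomy". Section 10.3.1 runs every safety analysis on that population.

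**The concern.** Two kinds of Arm A/B participant fall under two rules at once. One has neoadjuvant drug and RC but no adjuvant therapy. The other is never dosed but still has RC. Nothing in the protocol says which rule takes precedence.

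Both kinds are in the safety denominator. If a site applies the shorter clock, they count as fully observed there although systematic post-operative collection stopped early. Arm C is collected to 100 days after RC whether or not an event is judged related. Safety by arm is one of the few analyses that Amendment 04 keeps, so the meaning of a post-operative event count in each arm matters.

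**Working it through.** The plan gives no figure to reproduce; the check is date arithmetic on its own windows.

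**Inputs**
- The windows listed above.
- RC is due within 6 weeks (42 days) of the last neoadjuvant dose. A later date is possible after consultation, with no stated limit (Section 5.1.2.2).
- A post-surgery visit is required 60 to 90 days after RC (Table 2-3 and its footnote b).
- Adjuvant therapy starts 60 to 120 days after RC (Section 5.1.2.3).
- First dose is due within 3 calendar days of randomization (Table 2-2).

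**Neoadjuvant-only, last-dose clock.** Let g be the days from last dose to RC. Post-operative days covered = max(0, 100 − g), against 100 under Section 9.2.2.

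| g (days) | Covered | Short of 100 by |
|---|---|---|
| 21 | 79 | 21 |
| 28 | 72 | 28 |
| 42 | 58 | 42 |
| 56 (late RC) | 44 | 56 |

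Coverage ends before the post-surgery visit window opens when 100 − g < 60, that is, when g exceeds 40 days. RC at the 42-day limit meets this: exit on post-operative day 58, visit window from day 60. If exit waits for Follow-up Visit 2 at its latest (100 + 7 days), coverage is 107 − 42 = 65 days, still 35 short. Coverage reaches zero only if RC comes 100 days or more after the last dose.

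**Neoadjuvant-only, the other reading of Section 9.2.1.** That section counts from discontinuation of dosing, which need not be the last dose. If the decision to forgo adjuvant therapy is dated 60 days after RC, the window ends at 60 + 100 = 160 post-operative days. The same words can therefore end collection well before or well after RC plus 100 days. The Survival Status row of Table 2-4 is not ambiguous in this way: it names the last dose.

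**Never dosed, 30-day rule.** Let d be the day of RC counted from randomization. Post-operative days covered = max(0, 30 − d). The documents give no RC date for undosed Arm A/B participants, so d is an assumption.

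| d (assumed) | Covered |
|---|---|
| 14 | 16 |
| 21 | 9 |
| 28 | 2 |
| 30 or later | 0 |

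If the 6-week limit for Arm C were borrowed (d = 42), the window would close 12 days before surgery.

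**With the RC-based rule applied to both groups,** each has 100 post-operative days, as in Arm C.

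**The case against.** The best defence is that the larger group already has a specific rule. Section 9.2.2 and the Table 2-4 note both say RC plus 100 days, and the Amendment 03 change history describes the Section 9.2.2 wording as a clarification. A careful site would let the specific rule govern. Table 2-3 also collects events continuously, and related SAEs stay reportable after any window; Section 5.1.2.3 treats RC as protocol-specified surgery. The never-dosed group should be rare given the 3-day dosing rule, and enrollment has stopped.

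Much of this stands, and it rules out several stronger readings.

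- A reader might infer little or no post-operative capture for everyone who skips adjuvant therapy. With on-schedule RC, neoadjuvant-only participants keep about 58 days or more even on the shorter clock. Only the never-dosed can drop to a few days or none.
- A reader might infer that Arm A/B safety rates are biased downward against Arm C. The planned outputs are descriptive tabulations, procedure-related SAEs remain reportable, and Arms A and B are also observed through neoadjuvant and up to 12 adjuvant cycles. No net direction follows.
- A reader might infer that undosed participants never have non-serious AEs collected, because collection starts at study treatment. Sections 5.1 and 5.4.4 describe RC as part of study treatment, so the text does not settle this.

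The defence does not remove the conflict. The last-dose exit in Table 2-4 is current Amendment 04 text and cannot be followed together with RC plus 100 days when no drug is given after RC. The exit rules in the Synopsis and Section 5.1 require Section 9.2.3 to be satisfied, but that section covers follow-up of reported events, not how long new ones are sought. Late reporting depends on a relatedness judgement in an open-label trial, and Section 9.2.1 does not oblige investigators to seek events in former participants.

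**Conclusion.** The inconsistency is real and worth correcting; its effect is limited. Section 9.2.1 and the Table 2-4 exit rule disagree with Section 9.2.2 and the Table 2-4 adverse event note about Arm A/B participants who have RC and no later drug.

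- **Neoadjuvant-only:** about 58 of 100 post-operative days covered if RC is at 6 weeks and the last-dose clock is used. The exact loss depends on how discontinuation of dosing is read.
- **Never dosed with RC:** few or no post-operative days under the 30-day rule, depending on an RC date that the documents do not give. The group is probably small.

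What is at risk is systematic collection of events not judged related to drug or procedure. That makes post-operative capture non-comparable with Arm C. The documents give no count or share of participants affected, so the effect on any tabulated rate cannot be sized.

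**What to change.** 1. In Section 9.2.1, state that any Arm A/B participant who has RC and receives no later study drug has AEs and SAEs collected to 100 days after RC, as Section 9.2.2 and the Table 2-4 note already require.
2. Limit the 30-day rule to participants with neither study drug nor RC.
3. Align the Amendment 04 exit point with that window in the Survival Status row of Table 2-4, and give the Arm A/B exit rules in the Synopsis and Section 5.1 a stated starting point.

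Table 10.2-1 can stay as it is. The cost is wording, plus up to about six more weeks (42 days) of AE/SAE collection when RC is on schedule. A late RC adds more. For a never-dosed participant with RC on day d, SAE collection lengthens by (d + 100) − 30 = d + 70 days, for example 84 days if d = 14, in what is probably a small group.
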